### 5.1 Inclusion Criteria

1. Ability to provide informed consent and documentation of informed consent prior to initiation of any study-related tests or procedures that are not part of standard-of-care for the patient's disease. Patients must also be willing and able to comply with study procedures, including the acquisition of specified research specimens.
2. Age  $\geq$  18 years old.
3. Histologically proven, relapsed/refractory metastatic colorectal carcinoma.
4. Eastern Cooperative Oncology Group (ECOG) performance status of 0 or 1 ([Appendix 4](#)).
5. Life expectancy  $\geq$  12 weeks.
6. Measurable disease as per RECIST 1.1 criteria ([Appendix 5](#)) and documented by computed tomography and/or magnetic resonance imaging. Patients with evaluable disease only will not be enrolled on this study.

Note: Lesions to be used as measurable disease for the purpose of response assessment must either: a) not reside in a field that has been subjected to prior radiotherapy, or b) have demonstrated clear evidence of radiographic progression since the completion of prior radiotherapy and prior to study enrollment.

7. During the dose escalation portion of the study, patients must have had recurrence, progression or intolerance to standard therapy consisting of at least 2 prior standard regimens (containing a fluoropyrimidine plus a platinum analogue and/or irinotecan) for metastatic disease. During the Cohort Expansion portion of the study, patients will be allowed to participate in the study after 1 prior standard regimen. Patients who are inappropriate candidates for or have refused treatment with these regimens are also eligible. Patients should have received no more than 5 prior therapies. Patients previously treated with MGD007 on Study Protocol CP-MGD007-01 and who did not develop antibodies to MGD007 while on the CP-MGD007-01 study, may be enrolled. Patients that were previously treated on CP-MGD007-01 will only be treated on this study once MTD/MAD has been defined.

8. In addition, patients to be enrolled in the study must have an identified formalin-fixed, paraffin embedded tumor specimen and/or tumor specimens sufficient for 20 slides to enable determination of the expression of gpA33, CD3, PD-1, and PD-L1 within tumor specimens using immunohistochemical staining. The expression of gpA33 in tumor specimens will be analyzed retrospectively and will not be used to prospectively determine protocol eligibility.
9. For the 15 patients who will have paired tumor biopsies, tumor lesions must be accessible for biopsy with acceptable clinical risk in the judgment of the investigator. Paired tumor biopsies will be mandatory if tumor lesions are accessible for biopsy with acceptable clinical risk in the judgment of the investigator and after discussion with the Sponsor. Fifteen paired biopsies will be required in each cohort at the end of the Cohort Expansion Phase. For each patient, the identified lesion to be biopsied should not have been previously irradiated and should not be the only lesion being utilized as measurable disease target lesion for objective response assessment. The lesion to be biopsied should be of sufficient size to enable acquisition of at least 2 tumor biopsy cores using a biopsy needle.
10. Acceptable laboratory parameters as follows:
  - a. Platelet count  $\geq 100 \times 10^3$ /microliter without transfusion within 4 weeks prior to the initiation of study drug.
  - b. Hemoglobin  $\geq 8.0$  g/dL without transfusion within 1 week prior to the initiation of study drug.
  - c. White blood cell count (WBC)  $\geq 2.0 \times 10^3$ /microliter in the absence of any growth factor support within 4 weeks prior to the initiation of study drug.
  - d. Absolute neutrophil count  $\geq 1.5 \times 10^3$ /microliter in the absence of any growth factor support within 4 weeks prior to the initiation of study drug.
  - e. ALT/AST  $\leq 3.0$  times the ULN, up to 5.0 times the ULN for patients with liver metastases.
  - f. Total bilirubin  $\leq 1.5$  times ULN, except patients with Gilbert's syndrome, who may enroll if the conjugated bilirubin is within normal limits.
  - g. Creatinine  $< 1.5$  mg/dL, or a calculated or measured creatinine clearance  $> 50$  mL/min.
  - h. Negative urine or serum pregnancy test for women of child-bearing potential.
11. Female patients of childbearing potential (not surgically sterilized and between menarche and 1-year post menopause) must have a negative urine or serum pregnancy test performed within 72 hours prior to the initiation of study drug administration. If a patient is sexually abstinent but capable of becoming pregnant, she must agree to remain abstinent from the time of consent through 120 days after discontinuation of study drug administration. Should sexual activity commence, the patient must agree to use highly effective contraceptive measures from the time of consent through 120 days after discontinuation of study drug administration.

- a. Highly effective methods of contraception include hormonal contraceptives, intrauterine device or system, vasectomy, or tubal ligation. If a highly effective method is not achievable, then a “double barrier” method is an effective alternative in which the male partner must use a condom with spermicide and the female partner must use a diaphragm or cervical cap concurrently.
12. Male patients with partners of childbearing potential must use barrier contraception (i.e., condom). In addition, male patients should also have their partners use another method of contraception from the time of consent through 120 days after discontinuation of study drug administration.
13. Patients who are not pregnant or breastfeeding or expecting to conceive or father children within the projected duration of the study, starting with the prescreening or screening visit through 120 days after the last dose of study drug.

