### Summary of Changes in CP-MGD007-02 Original Protocol

Section	Summary of Main Changes and Rationale
Sponsor Signatures	████████████████████ as Medical Monitor for this program.
Sections 2, 4, 7, 9, and 14	Language with regards to the Q2W cohort was removed.
Section 4.1.1	The amount of treatment a patient must receive to be considered evaluable for the DLT evaluation period has been modified to 75% of both the required MGD007 doses and the required MGA012 doses.
Section 5.1	Inclusion criterion 7 was modified to include patients previously treated with MGD007 in Study Protocol CP-MGD007-01; stipulations were included.
Section 5.2	History of prior allogeneic bone marrow, stem-cell, or solid organ transplantation was added, as new Exclusion Criterion 3 and subsequent exclusion criteria were renumbered.
Section 5.5	Death had been inadvertently omitted in original protocol and has been added as this event should be included as a reason for patient discontinuation from a clinical study.
Section 6	Minor formulation adjustment in MGD007 drug product composition due to the addition of PS80 to the drug substance (DS) formulation. To maintain the same buffer strength, it required an adjustment to the sodium phosphate ratio and PS80 concentration in the DP formulation to account for the addition of PS80 in the DS buffer. In addition, there is clarification that allowable colors of MGA012 drug product solution may have a pale-yellow color. Edits were made within the subsections of this section: Sections 6.4.1, 6.4.3 and 6.4.6 .
Section 7.1	Guidelines for duration of prophylactic use of budesonide was amended to include a continuation of 5 days after MGD007 infusion, to better mitigate MGD007 adverse effects on the gastrointestinal tract and limit the use of dexamethasone.
Section 8.1.1	Text was included from a protocol change memo, CP-MGD007-02 Original Protocol, Change Memo 1 (dated 19 April 2018), regarding avoidance of the concomitant use of CYP450 substrates with a narrow therapeutic index during study treatment was added, given the potential for CYP enzyme suppression due to cytokine elevation.
Section 12.2.2	AESIs requiring reporting to the Sponsor within 24 hours were specifically listed for clarity, as provided in Section 12.2.4 .

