## 14.3 Demographics and Baseline Characteristics

Patient disposition, demographics, baseline characteristics, disease history, medical history, and prior cancer treatment will be summarized using descriptive statistics.

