## 14.6 Efficacy and Endpoint Analyses

### 14.6.1 Response Endpoints and Analyses

For RECIST v1.1, the best overall response (BOR) will be categorized as CR, PR, SD, PD, or NE. To be qualified as BOR, CR and PR require confirmation at least 4 weeks after initial observation of such response, and SD requires to be observed at least once after 8 weeks (minus 3 days) from the start of MGD007 treatment.

For irRECIST, the best overall response (BOR) will be categorized as irCR, irPR, irSD, irPD, or irNE. To be qualified as BOR, irCR, irPR, and irPD require confirmation at least 4 weeks after initial observation of such response, and irSD requires to be observed at least once after 8 weeks (minus 3 days) from the start of MGD007 treatment.

The objective response rate (ORR) per RECIST v1.1 is estimated as the proportion of patients in response evaluable population who achieve BOR of CR or PR. Disease control rate is calculated as the proportion of patients who achieve a CR, PR, or SD. Progression-free

survival rate at 16 weeks will be calculated as the probability that patients are free of disease progression and alive at 16 weeks after the first dose of MGD007 by Kaplan-Meier method described below, based on response evaluable population and safety population, respectively. The 2-sided 95% exact binomial CI of the response rates will be calculated. The response rates per irRECIST will be estimated similarly. Subgroup analyses of these response rates by KRAS gene type (wild and mutant) and by MMR status (MSS and MSI-H) will be performed.

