4 ANALYSIS POPULATIONS

4.1 Analysis Populations

The study analyses will be performed on the following populations:

- **Safety Population:** All patients who received at least one dose of any study drug. This population will be used for analyses of safety, PD, and immunogenicity. It will also be used for summary of baseline data and analyses of PFS and OS.
- **Response Evaluable Population:** All patients who received at least one dose of any study drug, had baseline measurable disease, and had at least one post-baseline radiographic tumor assessment or discontinued treatment due to clearly documented, clinically progressive disease or death. This population will be used for summary of tumor assessment data and analyses of response rates.

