6.8 Pharmacokinetic, Pharmacodynamic, and Immunological Parameter Endpoint Analyses

Pharmacokinetic Analysis: Summary statistics will be tabulated separately for serum PK parameters by MGD007 and MGA012 dose. Geometric means and percent coefficients of variation will be reported for C_{\max} , $AUC_{(0-T)}$, $AUC_{(TAU)}$, $AUC_{(INF)}$, and C_{trough} ; arithmetic means and standard deviations will be reported for $t_{1/2}$, CL, and V_{ss} ; and medians, minimum, and maximum will be reported for T_{\max} . Separate scatter plots of C_{\max} and AUC will be

provided versus dose to assess dose dependency. Dose proportionality may be assessed using a power model. Population PK analyses may be conducted using data from this study alone or combined with data from other studies.

Immunogenicity Analysis: The proportion of patients who are negative for ADA at baseline and become positive in this assay, the proportion of patients who are negative at baseline and remain negative, and those who have positive ADA at baseline that increases or decreases in titer over the course of treatment will be summarized. Analysis will be conducted separately for MGD007 and MGA012.

Pharmacodynamic Analysis: Summary statistics for pharmacodynamic parameters and corresponding changes from baseline will be summarized and/or may also be presented graphically as well as possible associations between changes in pharmacodynamic measures of interest and MGD007 in combination with MGA012 dose and exposure may be explored.

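### Patients who stayed antibody-negative on MGD007 in the earlier study may re-enrol and are pooled with MGD007-naive patients for MGD007 ADA and for efficacy, with no separate analysis

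*Protocol*

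**What the plan says.** **Who may enter.** Protocol 5.1, criterion 7, states that patients treated with MGD007 in CP-MGD007-01 "who did not develop antibodies to MGD007 while on the CP-MGD007-01 study, may be enrolled". It adds: "Patients that were previously treated on CP-MGD007-01 will only be treated on this study once MTD/MAD has been defined". The Amendment 1 summary of changes confirms that the criterion "was modified to include patients previously treated with MGD007 in Study Protocol CP-MGD007-01; stipulations were included". No cap or expected number is given.

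**How ADA is analysed.** SAP 6.8 summarises "The proportion of patients who are negative for ADA at baseline and become positive in this assay". The only split it states is by drug: "Analysis will be conducted separately for MGD007 and MGA012". The population is the Safety Population, meaning everyone who received any study drug; SAP 4.1 says "This population will be used for analyses of safety, PD, and immunogenicity". Protocol 14.2 and 14.5.2 agree.

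**How efficacy is analysed.** Objective response and disease control use the Response Evaluable Population. The 16-week PFS rate uses both that and the Safety Population. Protocol 14.6.1 states: "Subgroup analyses of these response rates by KRAS gene type (wild and mutant) and by MMR status (MSS and MSI-H) will be performed". SAP 6.6.1 repeats this, and PFS and OS are also broken down only by MMR and KRAS. The one SAP sensitivity analysis of PFS concerns censoring.

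**Prior therapy.** It appears only as a baseline summary: Protocol 14.3 says that "disease history, medical history, and prior cancer treatment will be summarized using descriptive statistics". SAP 6.3.2 does the same.

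**The concern.** The eligibility rule selects on the quantity that the immunogenicity analysis estimates. A patient who formed anti-MGD007 antibodies in the earlier study is kept out, and one who did not may come in. Once in, that patient counts in the MGD007 ADA summary alongside people who have never met the drug. The pooled proportion then no longer describes immunogenicity in MGD007-naive patients, which is how a reader would normally take it.

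The timing rule puts these patients mainly in the expansion of about 25. Immunogenicity is a secondary objective there (Protocol 3.2.2), and objective response, disease control and the 16-week PFS rate form the primary objective (Protocol 3.2.1). The efficacy estimates may therefore mix patients starting both drugs with patients who have already been treated with one of them. In a group this small, a handful of patients can move an estimate by several points.

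**Working it through.** **1. The plan's own figures.** Three dose levels of up to 9 patients give 3 × 9 = 27, and 27 + 25 = 52, as in Protocol 14.1. Table 13 reproduces with the Clopper-Pearson interval: lower limit = the 2.5% quantile of Beta(x, n − x + 1), upper limit = the 97.5% quantile of Beta(x + 1, n − x). For 5/25 this gives 6.8–40.7%, and the other five rows also match. The documents give no human ADA rate for MGD007 and no number of re-enrolled patients, so everything below on ADA is illustration under stated assumptions.

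**2. Formula.** With N patients, k of them prior-MGD007, naive rate p0 and prior-MGD007 rate p1:

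pooled rate = [(N − k)·p0 + k·p1] / N, so the shift from the naive rate is (k/N)·(p1 − p0).

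**3. ADA, assuming p0 = 30%.** SAP 4.1 names the Safety Population (about 52), while SAP 6.1 also provides for safety and efficacy summaries by expansion cohort (25). Both denominators are shown.

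| N | k | p1 = 5% | p1 = 30% | p1 = 45% |
|---|---|---|---|---|
| 25 | 5 | (20×0.30 + 5×0.05)/25 = 25.0% | 30.0% | (20×0.30 + 5×0.45)/25 = 33.0% |
| 25 | 10 | (15×0.30 + 10×0.05)/25 = 20.0% | 30.0% | (15×0.30 + 10×0.45)/25 = 36.0% |
| 52 | 5 | (47×0.30 + 5×0.05)/52 = 27.6% | 30.0% | (47×0.30 + 5×0.45)/52 = 31.4% |
| 52 | 10 | (42×0.30 + 10×0.05)/52 = 25.2% | 30.0% | (42×0.30 + 10×0.45)/52 = 32.9% |

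The first rate column is the expected case, where past non-formers tend to remain non-formers. The middle column is no selection effect. The last is re-exposure raising seroconversion to 1.5 times the naive rate. With k = 0 the shift is zero throughout.

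**4. Other naive rates, 25 patients.** If no prior-MGD007 patient seroconverts and k = 5, naive rates of 10%, 20% and 40% become 8.0%, 16.0% and 32.0%. With k = 10 they become 6.0%, 12.0% and 24.0%.

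**5. Response rate.** Protocol Table 2 shows 2 partial responses (one unconfirmed) in 59 evaluable patients on MGD007 alone: 2/59 = 3.4%. If prior-MGD007 patients responded at 3.4% and naive patients at an assumed 20%, then 5 of 25 gives (20×0.20 + 5×0.034)/25 = 16.7%, and 10 of 25 gives (15×0.20 + 10×0.034)/25 = 13.4%. The 3.4% comes from monotherapy and is no estimate of response to the combination on re-treatment. At an assumed 30% in prior-MGD007 patients, 5 of 25 gives (20×0.20 + 5×0.30)/25 = 22.0%. The direction is open.

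**6. Precision without these patients.** At the same 20% point estimate, 5/25 gives 6.8–40.7%, 4/20 gives 5.7–43.7% and 3/15 gives 4.3–48.1%.

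**The case against.** The strongest case against has four parts.

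- **There may be no such patients.** Enrolment is permitted, not planned. By the January 2018 data cut 75 patients had been treated in CP-MGD007-01; the criterion came in October 2018, and Protocol 2.2 cites median survival of 6.4 and 7.1 months on approved third-line agents. Candidates must also meet the performance-status, life-expectancy and prior-therapy limits. This stands: nothing supports any particular number, including the 5 and 10 used above.
- **The direction is not proven.** A reader might infer that ADA incidence is certainly biased low. The documents do not support that. A negative result in the earlier study may reflect short exposure (30 of 59 evaluable patients had progression as best response), and re-exposure could raise seroconversion. Low is the expected direction, no more.
- **The expansion was already mixed and is descriptive.** It takes MSS and MSI-H tumours, any KRAS status and varying prior therapy, tests no hypothesis, and has wide intervals. This stands against any claim that pooling ruins an otherwise uniform efficacy estimate. It does not answer the ADA point, where entry depends on the outcome itself.
- **Some safeguards exist.** Prior systemic therapy is on the eCRF (Protocol 9.5), and a pre-dose Cycle 1 Day 1 ADA sample is scheduled (Protocol Appendix 3). These make the patients identifiable and show who is positive at entry. They do not undo the selection, and no planned analysis uses them for this purpose.

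The SAP's silence is probably not a decision to pool: SAP 3.1 and 3.2 still describe two cohorts and 104 patients, the design before Amendment 1. Protocol section 14 nevertheless says the SAP governs, so pooling is what would follow from it.

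**Conclusion.** The point holds in a conditional form. Followed as written, the plan puts patients chosen for not forming anti-MGD007 antibodies into the same MGD007 ADA estimate as naive patients, and into the same efficacy estimates, with nothing to separate them.

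If any enrol, MGD007 ADA incidence is expected to come out too low. Under the assumed 30% and 5%, the shift is 5 or 10 points in a 25-patient expansion for 5 or 10 re-enrolled patients, and 2.4 or 4.8 points in a Safety Population of 52. It is zero if none enrol or the rates are equal, and upward if re-exposure raises seroconversion.

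Two wider readings are not supported. MGA012 ADA is not selected on by criterion 7. For response, disease control and PFS, the documents establish neither a direction nor a size of bias, only a mixture that the plan leaves unexamined. This is an inexpensive improvement to make before the data are seen, not a flaw that invalidates the study.

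**What to change.** When the SAP is brought into line with Amendment 1:

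- **SAP 6.8:** estimate MGD007 ADA incidence in MGD007-naive patients, state the denominator, and list prior-MGD007 patients separately with their baseline and on-treatment ADA results. The MGA012 ADA summary can stay as it is.
- **SAP 6.6:** add a sensitivity analysis of objective response rate, disease control rate and the 16-week PFS rate that excludes prior-MGD007 patients, under both RECIST 1.1 and irRECIST.
- **SAP 6.3.2:** report how many treated patients had prior MGD007, by phase.

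The cost is SAP wording and one extra row per table. Prior therapy and ADA samples are already collected, and eligibility and treatment are untouched. The naive-only intervals are slightly wider, for example 5.7–43.7% for 4/20 against 6.8–40.7% for 5/25. If no such patient enrols, the extra rows are empty and nothing is lost.

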## 4 STUDY DESIGN

### 4.1 Overall Study Design and Plan

[figure not shown]
This study is an open-label, Phase 1b/2 dose escalation and cohort expansion study designed to characterize the safety, tolerability, PK, pharmacodynamics, immunogenicity, and preliminary antitumor activity of MGD007 and MGA012, administered in combination by IV infusion, in patients with histologically proven, relapsed/refractory metastatic colorectal carcinoma, irrespective of the KRAS and MMR status of their tumors. This study will enroll patients as described below.

The study will proceed in 2 distinct phases as follows: Dose Escalation Phase to determine the MTD or MAD (if no MTD is defined) of the combination, followed by a Cohort Expansion Phase to further define the safety and initial antitumor activity of the combination with the doses established in the Dose Escalation Phase.

Patients will be treated with MGD007 and MGA012 as shown in [Figure 11](#). MGD007 will be administered at the target dose for each assigned cohort as an IV infusion over 120 minutes, once weekly (QW), in 8-week treatment cycles. MGA012 will be administered at 3 mg/kg as an IV infusion over 60 minutes, once every 2 weeks (Q2W) beginning on Cycle 1 Day 15, and every 2 weeks thereafter. For each patient, administration of the first dose of MGA012 will occur 2 weeks after the first dosing of MGD007. The DLT evaluation period will last until Cycle 1 Day 42. Disease status will be evaluated on Cycle 1 Day 56 ( $\pm$  3 days) using CT and/or MRI as appropriate for the sites of disease, accompanied by physical examination, and will then be evaluated every 8 weeks while on study treatment. Although response assessment will be performed according to both conventional (RECIST 1.1 [\[Appendix 5\]](#)) and irRECIST ([Appendix 6](#)), patients will be managed according to irRECIST principles. This approach allows for limited treatment of patients beyond the initial radiographic documentation of disease progression, assuming that the Investigator feels that the patients are tolerating therapy adequately, that patients remain otherwise clinically stable despite this initial radiographic evidence of disease progression, and that the Investigator feels the patient may still derive benefit from continuation of therapy.

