## 7.5.1 Hepatic Toxicity

### 7.5.1.1 Elevations in Transaminases

Treatment management algorithm for patients experiencing hepatic toxicity are as follows:

- Grade 1 elevations - No specific therapy required.
- Grade 2 elevations - For elevations in transaminases 3 to  $5 \times$  ULN, rule out viral and other etiologies, and consider immediate oral steroids such as prednisone 60 mg/day divided twice daily, and hold MGD007 and MGA012.
  - If improvement to  $\leq$  Grade 1 does not occur within 48 hours consider IV steroids such as methylprednisolone at 2 mg/kg/day divided twice daily or oral steroids such as prednisone 60 to 120 mg per day, divided twice daily.
  - Resume MGD007 and MGA012 at the next scheduled dose if no more than 2 doses of the combination were missed.
  - If improvement to  $\leq$  Grade 1 does not occur within 14 days, discontinue MGD007 and MGA012.
- Grade 3 elevations - Hold MGD007 and MGA012.
  - For elevations in transaminases  $> 8 \times$  ULN, permanently discontinue MGD007 and MGA012.
    - Begin immediate IV steroids, and
    - If no response to corticosteroid therapy within 3 to 5 days is observed, consider adding immune suppression therapy with mycophenolate.
    - Monitor liver function tests at least twice weekly (or more frequently as clinically appropriate in the judgment of the Investigator) until transaminases have returned to Grade 1 or baseline.
  - For elevations in transaminases  $> 5$  but  $\leq 8 \times$  ULN:

- Begin immediate IV steroids; suggest methylprednisolone at a dosage of 2 mg/kg/day divided twice daily.
- Consider additional immune suppression as above for patients who do not respond to corticosteroid therapy within 3 to 5 days.
- Monitor liver function tests at least twice weekly (or more frequently as clinically appropriate in the judgment of the Investigator) until transaminases have returned to Grade 1 or baseline.
- If the elevation does not improve to Grade 2 within 7 days and to Grade 1 within 14 days, discontinue MGD007 and MGA012.
- Resume MGD007 and MGA012 administration if following conditions are met:
  - Laboratory elevations downgrade to  $\leq$  Grade 2 within 7 days and improve to  $\leq$  Grade 1 or baseline within 14 days.
  - Steroids have been tapered to  $\leq$  10 mg per day of prednisone or equivalent.
  - On resuming MGD007 and MGA012, AST, ALT, and total and direct bilirubin laboratory test values will be evaluated at least once per week for 3 consecutive weeks.

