## 7.5.2 Elevations in Total Bilirubin

Management guidelines for patients experiencing elevations in total bilirubin are as follows:

- Grade 1 elevations - No specific therapy required.
- Grade 2 elevations - Hold MGD007 and MGA012 until improvement to  $\leq$  Grade 1.
  - Consider oral steroids.
  - If improvement to  $\leq$  Grade 1 does not occur within 14 days, discontinue MGD007 and MGA012 and begin oral steroids.
- Grade 3 elevations - Hold MGD007 and MGA012
  - For elevations in total bilirubin  $> 5 \times$  ULN, permanently discontinue MGD007 and MGA012 and initiate IV steroids, suggest methylprednisolone at a dosage of 2 mg/kg/day divided twice daily, and,

- If no response to corticosteroid therapy within 3 to 5 days is observed, consider adding immune suppression therapy with mycophenolate.
- Monitor liver function testing at least twice weekly (or more frequently as clinically appropriate in the judgment of the Investigator) until total bilirubin has returned to Grade 1 or baseline.
- For elevations in total bilirubin  $> 3.0$  but  $\leq 5 \times \text{ULN}$ :
  - Begin immediate IV steroids, suggest methylprednisolone at a dosage of 2 mg/kg/day divided twice daily. Consider additional immune suppression as above for patients who do not respond to corticosteroid therapy within 3 to 5 days.
  - Monitor liver function including total bilirubin testing at least twice weekly (or more frequently as clinically appropriate in the judgment of the Investigator) until total bilirubin has returned to Grade 1 or baseline.
  - If the elevation does not improve to Grade 2 within 7 days and to Grade 1 within 14 days, discontinue MGD007 and MGA012.
- Resume MGD007 and MGA012 administration if:
  - Laboratory elevations downgrade to  $\leq$  Grade 2 within 7 days and improve to  $\leq$  Grade 1 or baseline within 14 days.
  - Steroids have been tapered to  $\leq 10$  mg per day of prednisone or equivalent.
  - On resuming MGD007 and MGA012, AST, ALT, and total bilirubin laboratory test values will be evaluated at least once per week for 3 consecutive weeks.
- Permanently discontinue MGD007 and MGA012 in the case of a second increase of total bilirubin to  $\geq$  Grade 3.
- Grade 4 elevations - Discontinue MGD007 and MGA012 and treat as for Grade 3 elevation. MGD007 and MGA012 should be permanently discontinued.

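### Eligibility admits liver-metastasis patients throughout the Grade 2 AST/ALT band, but the Grade 2 stop rule and the hepatic DLT definition require Grade 1 with no baseline term, so full recovery to entry level still fails both

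*Protocol*

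**What the plan says.** **Entry.** Protocol Section 5.1, criterion 10e, caps AST/ALT at 3.0 times ULN but allows "up to 5.0 times the ULN for patients with liver metastases". Criterion 10f caps total bilirubin at 1.5 times ULN. It exempts patients with Gilbert's syndrome whose conjugated bilirubin is normal, and sets no upper limit on their total bilirubin.

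**Grade 2 management.** Section 7.5.1.1 applies its Grade 2 branch to transaminases at 3 to 5 times ULN. Sites are told to "consider immediate oral steroids such as prednisone 60 mg/day divided twice daily, and hold MGD007 and MGA012". If improvement to no worse than "Grade 1 does not occur within 14 days, discontinue MGD007 and MGA012". For Grade 2 total bilirubin, Section 7.5.2 also holds both drugs. If improvement to Grade 1 or lower "does not occur within 14 days, discontinue MGD007 and MGA012 and begin oral steroids".

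**Grade 3 management.** For transaminases above 5 and up to 8 times ULN, Section 7.5.1.1 has a stop bullet that requires Grade 2 within 7 days and Grade 1 within 14. Its resume bullet accepts either Grade 1 or baseline within 14 days. Section 7.5.2 has the same pair of bullets for bilirubin above 3 and up to 5 times ULN.

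**DLT.** Section 4.2.3 counts a Grade 3 transaminase or bilirubin elevation in those same ranges as a DLT unless it resolves to Grade 2 within 7 days and Grade 1 within 14. It has no baseline term. It also gives the grade bands: transaminase Grade 2 is above 3.0 to 5.0 times ULN, and bilirubin Grade 2 is above 1.5 to 3.0 times ULN.

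**The concern.** The entry criterion treats a raised value as acceptable in a patient whose liver metastases may explain it. The stop rule and the DLT definition judge recovery on an absolute scale that such a patient did not meet on entry. Returning to the pre-treatment state, the most that can ordinarily be expected after a drug effect clears, does not satisfy either one.

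Two things are at stake. A recovered patient can lose both study drugs because of a value that predates treatment. A hepatic event that has reversed completely can also enter the DLT count, and that count decides escalation and the MTD, which is part of the primary objective of the Dose Escalation Phase. Because the sections disagree, sites may handle the same patient differently.

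**Working it through.** No sample size or power figure bears on this point. The check compares the ranges and follows illustrative patients through the rules.

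**1. Overlap of the ranges (multiples of ULN)**

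| Item | Source | Range or target |
|---|---|---|
| Extra AST/ALT entry range with liver metastases | Section 5.1, 10e | above 3.0 to 5.0 |
| Transaminase Grade 2 | Section 4.2.3 | above 3.0 to 5.0 |
| Hold both drugs, Grade 2 | Section 7.5.1.1 | 3 to 5 |
| Level needed by 14 days to avoid stopping | Section 7.5.1.1 | 3.0 or lower (Grade 1) |

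The extra range opened by 10e is exactly the Grade 2 band. Every patient admitted under it starts above the level that the stop rule requires.

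**2. A rise within Grade 2**

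Entry is at 3.5, the on-study value is 4.5, and it returns to 3.5 within 14 days.
- The rise above entry is 4.5 − 3.5 = 1.0, and it has fully reversed.
- The criterion is 3.0 or lower; 3.5 exceeds it, so both drugs are discontinued.
- The Grade 2 resume bullet counts only missed doses and names no laboratory level, so it does not override the 14-day stop.

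**3. A rise into Grade 3**

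Entry is at 4.0, the on-study value is 6.0 and judged drug-related, and it returns to 4.0 within 7 days. Steroids are assumed tapered as required.
- Grade 2 within 7 days: met (4.0 is not above 5.0).
- Grade 1 within 14 days: not met (4.0 is above 3.0).
- Section 7.5.1.1 stop bullet: discontinue.
- Section 7.5.1.1 resume bullet: resumption allowed, because the value is back at baseline.
- Section 4.2.3: counts as a DLT if it falls in the window to Cycle 1 Day 42. Section 5.4 lists a drug-related DLT among the conditions for stopping treatment, which again conflicts with the resume bullet.

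Patients admitted under the exception also reach Grade 3 more easily. From 3.0, a value must rise by a factor of 5.0/3.0 = 1.67; from 5.0, any rise is enough.

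**4. What one such DLT does under Section 4.3**

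| DLTs without the event | Decision | DLTs with it | Decision |
|---|---|---|---|
| 0 of 3 | escalate | 1 of 3 | expand to 6 |
| 1 of 3 | expand to 6 | 2 of 3 | MTD exceeded |
| 1 of 6 | escalate | 2 of 6 | expand to 9 |
| 2 of 6 | expand to 9 | 3 of 6 | MTD exceeded |
| 2 of 9 | MTD not exceeded | 3 of 9 | MTD exceeded |

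A single event changes the decision in every row.

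**5. Bilirubin**

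A Gilbert's patient enters at 2.0 with normal conjugated bilirubin, rises to 2.5 and returns to 2.0. Grade 1 ends at 1.5, so Section 7.5.2 requires discontinuation and oral steroids at 14 days. A rise to between 3 and 5 that returns to 2.0 meets the Section 7.5.2 resume bullet, fails its stop bullet and, if drug-related and within the window, is a DLT under Section 4.2.3. Neither section mentions Gilbert's syndrome.

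**The case against.** The best defence is scope. Section 7.5 concerns immune-related events and speaks of interruption for treatment-related toxicity. Section 7.5.1.1 is addressed to patients with hepatic toxicity and asks sites to rule out other causes. Section 12.1.1 includes occurrences that are new or worse than at baseline. A value already known at screening is neither new nor caused by study drug, so a site can admit a patient at 4 times ULN and apply the rules only to later changes.

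This stands for a patient whose values never change. A reader might infer that such a patient necessarily meets the stop rule before any MGA012, since "administration of the first dose of MGA012 will occur 2 weeks after the first dosing of MGD007" and a hold from Day 1 reaches 14 days on Day 15. The documents do not compel that: the scope wording reasonably exempts the patient, although no section says so for this trigger.

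A reader might also infer that such patients dilute PFS and OS in the Safety Population, or need replacement. Neither follows. A literal hold from Day 1 means no dose of either drug, and the Safety Population requires at least one. Section 4.1.1 replaces under-dosed patients only when the cause is unrelated to treatment, whereas Section 7.5 deals with treatment-related toxicity.

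The scope argument does not reach a patient whose values do rise on study. That is a change from baseline and can be attributed to drug, and the recovery target is still Grade 1. For potentially dose-limiting toxicity, Section 4.4.1 ties restart to resolution under Section 7 even when the event is judged unrelated. Section 5.4 permits case-by-case continuation, but for compelling clinical benefit, and the first scheduled scan is at Cycle 1 Day 56.

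**Conclusion.** The concern holds for patients admitted with raised liver tests who then have an on-study rise. If they return fully to their entry level, Section 7.5.1.1 or 7.5.2 still requires both drugs to stop. If the rise was drug-related, within the DLT window and into the Grade 3 ranges in Section 4.2.3, it also counts as a DLT. The Grade 3 stop and resume bullets give opposite instructions for the same patient.

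For the individual, the consequence is loss of both drugs. For the trial, one such DLT can change an escalation decision. How often this would happen cannot be derived: the documents give no proportion of patients expected to enter above 3 times ULN, or with Gilbert's syndrome above 1.5 times ULN. Listing the liver among common metastatic sites in Section 2.2 does not supply one. The conflict in the text does not depend on that number.

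The DLT part assumes that the investigator attributes the rise to study drug. Elevations above 8 times ULN for transaminases, or 5 times for bilirubin, count whatever their duration and are unaffected. This should be corrected, but it does not invalidate the design.

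**What to change.** The sponsor should reconcile Sections 5.1 (10e and 10f), 7.5.1.1, 7.5.2 and 4.2.3 so that eligibility, the hold, stop and resume rules, and the hepatic DLT criteria treat an eligible raised baseline consistently. Within Sections 7.5.1.1 and 7.5.2, the Grade 3 stop and resume bullets must agree with each other. The text should also say whether an unchanged entry value triggers the Grade 2 rule. Which limit or rule is right is the sponsor's clinical decision.

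If baseline is used as a reference, it should be defined. SAP Section 6.1 already defines it as the last value before the first MGD007 dose. Any hepatic DLT should be reported with the patient's entry value, so that its part in an escalation decision can be seen.

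The cost is wording in a protocol amendment. Liver tests are already taken at screening and before infusions, so no procedure or visit is added.
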